## 7.5 Adjustments for Multiple Comparisons

No adjustments will be made for multiple comparisons because the three cohorts are enrolled and analyzed completely independently from each other. No results or conclusions will be derived from the three cohorts together.

## 7.6 Demographic and Other Baseline Characteristics

Demographics and Baseline characteristics will be summarized for each cohort separately for all enrolled subjects using the FAS.

Demographics and other Baseline characteristics summarized will include:

For NOUR cohort only:

- Baseline self-catherization per day
- [REDACTED]
- [REDACTED]
- [REDACTED]

## 7.7 Treatment Characteristics

## 7.8 Interim Analyses

There is no planned interim analysis for this study.

## 7.9 Evaluation of Objectives

### 7.9.1 Overactive Bladder Cohort

#### 7.9.1.1 Primary objective

The primary objective for overactive bladder cohort of the study is to demonstrate there is an improvement in Overactive Bladder Quality of Life (OAB-q) Questionnaire Health Related Quality of Life (HRQL) total score at 3 months post-implant compared to Baseline.

Change on OAB-q HRQL at 3 months post-implant compared to Baseline will be calculated as the difference between average of total score at 3 months post-implant visit and at Baseline. This will be calculated for each subject and the average change will be reported with descriptive statistics.

Positive values represent an improvement in OAB-q HRQL total score.

#### 7.9.1.2 Hypothesis

The null ( $H_0$ ) and alternative ( $H_1$ ) hypotheses are:

$$H_0: \mu = 0$$

$$H_a: \mu \neq 0$$

Where  $\mu$  indicates the mean change in OAB-q HRQL total score from Baseline to 3 months post-implant. P-value will be evaluated at alpha level of 0.05.

#### 7.9.1.3 Experimental Design

Subjects will complete the Overactive Bladder Quality of Life Questionnaire (OAB-q) at Baseline, Three-month, [REDACTED] The Overactive Bladder Quality of Life Questionnaire (OAB-q) is a 33-item validated questionnaire that was developed to assess symptom bother and the impact of overactive bladder (OAB) on health-related quality of life (HRQL). The questionnaire used in the current study includes a 4-week recall for symptom assessment.

#### 7.9.1.4 Analysis Methods and Presentation Format

In case the normality assumption of data will hold (Shapiro Will test), a two-sided one sample t-test will be performed to test the hypothesis described in section 7.9.1.2.

In case the normality assumption of data will not hold (Shapiro Will test), a Wilcoxon Singed Rank test will be performed to test the hypothesis described in section 7.9.1.2.

In addition to the hypothesis testing, the two-sided 95% confidence interval for the mean change in HRQL total score will be calculated and reported.

In cases where subject's OAB-q HRQL total score is missing at Baseline and/or at 3 months post-implant for any reasons, the percentage of missing data will be summarized and a sensitivity analysis using multiple imputation will be performed as described in section 7.4.

### 7.9.1.5 Determination of Subject for Analysis

The primary analysis will include all complete case subjects (CC) who have data available at Baseline and Three-months follow up visit. Sensitivity analysis will include all implanted subjects (FAS) by imputing missing data as described in section 7.4.

### 7.9.1.6 Additional Measure

A high-resolution grayscale image of a handwritten digit, specifically the number 4, centered on a white background. The digit is rendered in a dark gray or black color, showing significant texture and stroke detail. The background is a uniform white, and the overall image has a clean, professional appearance, likely a scan of a printed document.

The image consists of a series of horizontal black bars of varying lengths and positions on a white background. The bars are arranged in a staggered, non-overlapping manner. Some bars are longer and centered, while others are shorter and positioned towards the edges. The overall effect is reminiscent of a digital interface or a minimalist abstract artwork.

### 7.9.2 Fecal Incontinence Cohort

### 7.9.2.1 Primary objective

The primary objective for fecal incontinence cohort of the study is to demonstrate there is an improvement in Cleveland Clinic Incontinence Score (CCIS) at 3 months post-implant compared to Baseline. Change on CCIS at 3 months post-implant compared to Baseline will be calculated as the difference between average of total score at 3 months post-implant visit and at Baseline. This will be calculated for each subject and the average change will be reported with descriptive statistics.

Negative values for a change from Baseline represent a decrease in CCIS and positive values represent an increase in CCIS.

### 7.9.2.2 Hypothesis

The null ( $H_0$ ) and alternative ( $H_1$ ) hypotheses are:

$$H_0: \mu = 0$$

$$H_a: \mu \neq 0$$

Where  $\mu$  indicates the mean change in CCIS from Baseline to 3 months post-implant. P-value will be evaluated at alpha level of 0.05.

### 7.9.2.3 Experimental Design

Subjects will complete the Cleveland Clinic Incontinence Score (CCIS) at Baseline, Three-month,

The Cleveland Clinic Incontinence Score (Wexner Score) is an established 5-item questionnaire that was developed to assess the frequency and severity of fecal incontinence.

This questionnaire will be completed by the subject at Baseline, Three-month,

#### 7.9.2.4 Analysis Methods and Presentation Format

In case the normality assumption of data will hold (Shapiro Will test), a two-sided one sample t-test will be performed to test the hypothesis described in section 7.9.1.2.

In case the normality assumption of data will not hold (Shapiro Will test), a Wilcoxon Singed Rank test will be performed to test the hypothesis described in section 7.9.1.2.

In addition to the hypothesis testing, the two-sided 95% confidence interval for the mean change in CCIS will be calculated and reported.

In cases where subject's CCIS is missing at Baseline and/or at 3 months post-implant for any reasons, the percentage of missing data will be summarized and a sensitivity analysis using multiple imputation will be performed as described in section 7.4.

### 7.9.2.5 Determination of Subject for Analysis

The primary analysis will include all complete case subjects (CC) who have data available at Baseline and Three-months follow up visit. Sensitivity analysis will include all implanted subjects (FAS) by imputing missing data as described in section 8.4.

### 7.9.2.6 Additional Measure

A horizontal bar chart consisting of five solid black bars of varying lengths. The bars are arranged from left to right in increasing order of height. The first bar is the shortest, followed by a tall bar, a medium bar, a short bar, and a very tall bar. The bars are set against a white background with no grid lines.

A 10x10 grid of black bars on a white background. The bars are of varying lengths and are positioned in a staggered, non-overlapping manner. The lengths of the bars decrease from left to right across each row and increase from top to bottom within each column.

### 7.9.3 Non-Obstructive Urinary Retention Cohort

#### 7.9.3.1 Primary objective

The primary objective for the non-obstructive urinary retention cohort of the study is to demonstrate an improvement in number of clean intermittent self-catheterizations (CISC) per day at 3 months post-implant compared to Baseline.

Change on the number of CISC per day at 3 months post-implant compared to Baseline will be calculated as the difference between average number of CISC per day at 3 months post-implant visit and at Baseline. This will be calculated for each subject and the average change will be reported with descriptive statistics.

Negative values for a change from Baseline represent a decrease in the number of CISC per day and positive values represent an increase in the number of CISC per day.

#### 7.9.3.2 Hypothesis

The null ( $H_0$ ) and alternative ( $H_1$ ) hypotheses are:

$$H_0: \mu = 0$$

$$H_a: \mu \neq 0$$

Where  $\mu$  indicates the mean change in the number of CISC per day from Baseline to 3 months post-implant. P-value will be evaluated at alpha level of 0.05.

#### 7.9.3.3 Experimental Design

Subjects will be trained to complete the urinary voiding diaries for 7-days for NOUR with diary details collected (such as time, type of episode, volume, etc.) as part of the Baseline procedures. The urinary voiding diaries will be completed for 7-days for NOUR towards the end of the therapy evaluation and prior to each subsequent follow-up visit. Every effort should be made to remind subjects of the importance of real-time diary completion.

#### 7.9.3.4 Analysis Methods and Presentation Format

In case the normality assumption of data will hold (Shapiro Will test), a two-sided one sample t-test will be performed to test the hypothesis described in section 7.9.3.2.

In case the normality assumption of data will not hold (Shapiro Will test), a Wilcoxon Singed Rank test will be performed to test the hypothesis described in section 7.9.3.2.

In addition to the hypothesis testing, the two-sided 95% confidence interval for the mean change in number of CISC will be calculated and reported.

In cases where subject's number of CISC per day is missing at Baseline and/or at 3 months post-implant for any reasons, the percentage of missing data will be summarized and a sensitivity analysis using multiple imputation will be performed as described in section 7.4.

### 7.9.3.5 Determination of Subject for Analysis

The primary analysis will include all complete case subjects (CC) who have data available at Baseline and Three-months follow up visit. Sensitivity analysis will include all implanted subjects (FAS) by imputing missing data as described in section 7.4.

### 7.9.3.6 Additional Measure

A horizontal bar chart consisting of 10 bars. The bars are black and are arranged in a descending order of length from left to right. The first bar is the longest, and the tenth bar is the shortest. There is a small gap between the first bar and the second bar, and a larger gap between the second bar and the third bar. The bars are set against a white background.

## 7.10 Safety Evaluation

All serious, device-related, procedure-related and/or therapy-related AEs and all DDs will be considered reportable for this study. All reportable AEs and DDs will be collected throughout the study once the informed consent form is signed. AEs and DDs will be coded and summarized using the Medical Dictionary for Regulatory Affairs (MedDRA). Serious AEs will be summarized for all consented subjects (Consent Subject Set), all subjects who go through lead placement procedure, as well as separately prior to INS implant (Test Subject Set) and after INS implant (Full Analysis Set). Device-related, procedure-related and/or therapy-related AEs and DDs will be summarized for all subjects who go through lead placement procedure, as well as separately prior to INS implant (Test Subject Set) and after INS implant (Full Analysis Set). For safety evaluation after INS implants, it will be summarized for subjects with INS implant only. The severity, treatment needed, resolution, and relevant principal investigator's judgment concerning the causal relationship with the devices or procedure or therapy will be provided as listing. The number of events, the number of subjects who experience an event, and the percentage of subjects who experienced one or more events will be summarized for each cohort as well as pooled for the three cohorts together. A listing of deaths and reasons for deaths will be provided for each cohort as well as pooled for the three cohorts together, if any death occur in the study.

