## 6. Study Design

This is a prospective, multicenter, global, single arm, post market clinical follow-up study to confirm the clinical performance and safety of the InterStim Micro system. Commercial devices will be used within their intended use as described in each geography's approved instructions for use.

Eligible subjects, who are already candidates for sacral neuromodulation, will sign a study-specific informed consent form (ICF). All eligible subjects will complete baseline procedures, including a baseline diary [REDACTED] prior to the evaluation lead implant procedure. Subjects must be screened and qualify to enroll in a single cohort of the study. Following the therapy evaluation lead implant, subjects are expected to complete a study diary near the end of the therapy evaluation period. Upon completion of a successful therapy evaluation period, subjects will have a neurostimulator implant procedure. Subjects will be considered enrolled at the completion of the neurostimulator implant procedure. Study requirements, including diaries, questionnaires and safety assessments will be completed as required in section 9.1. Study follow-up is expected to last approximately 2 years following the neurostimulator implant visit. Subjects will be exited from the study after the Two-Year Follow-up Visit is completed. Any subjects that have the device permanently explanted during follow up will be exited from the study.

A minimum of 50 subjects who complete the Three-month Follow-up Visit is required for the overactive bladder and fecal incontinence cohorts. A minimum of 30 subjects who complete the Three-month Follow-up Visit is required for the non-obstructive urinary retention cohort. Each subject will only be qualified for one of the study cohorts.

The study is intended to be conducted at approximately 40 centers in Europe, Canada, Australia and the United States (and United States Territories).

This is an on-label, post-market study of an approved system. All subjects implanted in the study will qualify under the approved indications for sacral neuromodulation.

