##### Medtronic Controlled Information

$H_a: \mu \neq 0$ 

Where  $\mu$  indicates the mean change in OAB-q HRQL total score from baseline to 3 months post-implant.

The power calculations were performed using PASS 11 statistical software. Based on the results of HRQL in OAB-q at 3 months post-implant reported in the InSite study, a mean score change of 30 at 3 months from baseline with the standard deviation of 27 are the assumptions used for the power calculation for this study. At an alpha level of 0.05, a sample size of 50 evaluable subjects results a power greater than 90% for this cohort.

The HRQL module and its subscales for International Consultation on Incontinence Questionnaire (ICIQ)-OABqol and OAB-q questionnaires are the same measures.

The attrition between implant and the primary endpoint at the 3-month Follow-up Visit is expected to be less than 10%. To accommodate attritions between implant and 3-month Follow-up Visit as well as during long-term follow-up, approximately 60 subjects will be implanted for this cohort. Based on historical Medtronic sponsored SNM studies (InSite study and SNS bowel), attrition at 2 year long-term follow-up visits is typically around 20%. Therefore, we expect attrition in this post-market study to be similar. In all cases of missing data, the reason will be collected and sensitivity analyses will be performed to evaluate the impact of missing data on primary objective.

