## 13.7. Safety Assessment

To characterize safety during the study duration.

To characterize safety of the InterStim Micro System by summarizing the adverse device effects and serious adverse device effects during the study. Safety measures will be summarized for each cohort as well as pooled for all patients regardless of indication. Device deficiencies will also be collected and reported.

Summaries will be presented as number of serious events, number of events, number of subjects who experienced the event, and percent of subjects who experienced the event. All adverse events and device deficiencies will be reported for each cohort as well as pooled for the three cohorts together.

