#### **7.1.3 Analysis Sets**

- The **Consented Subject Set** includes all subjects who signed the study-specific informed consent form (ICF).
- The **Test Subject Set** includes all subjects who underwent a lead placement attempt, whether the procedure was successful or not.
- The **Full Analysis Subject Set (FAS)** includes all subjects who signed the study-specific ICF and enrolled in the study. Subjects are considered enrolled at completion of the neurostimulator implant procedure.

- The **Complete Case Subject Set (CC)** consist of the subjects implanted with the Neurostimulator Device (Enrolled) and who have data available at Baseline and at each follow up visit.

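### Post-implant safety is planned as crude percentages of all implanted subjects, with no allowance for follow-up time; read as 2-year risks, these run low

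*SAP*

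**What the plan says.** SAP 7.10 reports the number of events, the number of subjects with an event, and a percentage: "the percentage of subjects who experienced one or more events will be summarized for each cohort as well as pooled". Protocol 13.7 has the same measures: "number of subjects who experienced the event, and percent of subjects who experienced the event".

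The post-implant denominator is set in SAP 7.10: "For safety evaluation after INS implants, it will be summarized for subjects with INS implant only". That group is the Full Analysis Set, which SAP 7.1.3 says "includes all subjects who signed the study-specific ICF and enrolled in the study", enrolment being completion of the neurostimulator implant. Length of follow-up plays no part in the definition.

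Four other places bear on the point:

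- Protocol 13.1.1 says for each cohort that "attrition at 2 year long-term follow-up visits is typically around 20" per cent, and that less than 10% is expected by the 3-month visit.
- Protocol 9.6 collects reportable events from consent until the subject exits.
- Protocol 6 ends participation at permanent explant: "Any subjects that have the device permanently explanted during follow up will be exited from the study".
- Protocol 4.2 gives confirmation of long-term performance and safety as the purpose, while the primary objectives stop at 3 months.

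Neither safety section mentions cumulative incidence, person-time rates, numbers at risk, or a rule for subjects who leave early. Many additional measures are blacked out, but SAP 7.10 and Protocol 13.7 are not, so this gap is not a redaction.

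**The concern.** A subject lost at month 4 without an event stays in the denominator for the whole study, yet nothing that happens to that subject afterwards can reach the numerator. The crude percentage therefore mixes the event risk with the chance of still being followed when the event occurs. When loss is unrelated to event risk, this can only lower the figure.

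The stake is the main long-term product of the study. Readers will naturally take the percentage with an ADE or SADE in a study with 2-year follow-up as a 2-year risk, and Protocol 6.2 allows performance data from the study to support claims. As written, the SAP offers no estimate that carries that meaning.

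**Working it through.** **What there is to reproduce.** The documents give no safety event rate and no safety precision, so there is no planned safety figure to check. From the plan's own attrition, subjects still followed at 2 years would be 60 × 0.80 = 48 (OAB), 48 (FI) and 40 × 0.80 = 32 (NOUR), or 128 of 160.

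**Inputs.** Attrition at 24 months is A = 0.20, and attrition by month 3 is at most 0.10 (both Protocol 13.1.1). The true 2-year risk R is an assumption: 20% is used below and 5% to 30% was examined.

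**Formula.** Let F(t) be the distribution of time to first event and G(t) the probability of still being followed at t, independent of the event. The expected crude percentage at 24 months is the integral of G(t) dF(t) from 0 to 24. The target is F(24) = R. G never exceeds 1 and never falls below 0.80 before 24 months, so the crude figure lies between 0.80 × R and R.

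**Base case, constant hazards.** The event hazard is −ln(0.80)/24 per month. With 20% attrition the dropout hazard is the same.

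Crude = [h_event / (h_event + h_drop)] × [1 − exp(−(h_event + h_drop) × 24)] = 0.5 × (1 − 0.80 × 0.80) = 0.5 × 0.36 = 18.0%.

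That is 2.0 points, or 10% in relative terms, below 20%. If the 20% leave at times spread evenly over 2 years instead, crude = 0.80 × 0.20 + 0.20 × [1 − 0.20/0.2231] = 0.160 + 0.021 = 18.1%, where 0.2231 = −ln(0.80).

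**Event timing and dropout timing** (R = 20%, numerical integration, relative bias in brackets):

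| Event hazard | Constant dropout | 10% gone by month 3 |
|---|---|---|
| Constant | 18.0% (−10%) | 17.3% (−14%) |
| Half of it in the first 3 months | 18.8% (−6%) | 18.1% (−10%) |
| 80% of it in the first month | 19.5% (−2%) | 19.2% (−4%) |
| Rising with time (cumulative hazard proportional to t²) | 17.3% (−13%) | 16.8% (−16%) |

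The bound, with every loss at day 0, is 0.80 × 20% = 16.0% (−20%). The relative bias hardly depends on R: under constant hazards it is −10.3% at R = 5% and −9.8% at R = 30%.

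**Explant.** A permanently explanted subject is no longer at risk from the implanted device, so explant acts largely as a competing event. If a share x of the attrition hazard is explant, the correct cumulative incidence is [h_event / (h_event + x·h_drop)] × [1 − exp(−(h_event + x·h_drop) × 24)]:

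| Share of attrition that is explant | Cumulative incidence | Crude |
|---|---|---|
| 0% | 20.0% | 18.0% |
| 25% | 19.5% | 18.0% |
| 50% | 19.0% | 18.0% |
| 100% | 18.0% | 18.0% |

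A Kaplan-Meier curve that censors explants would show 20.0% in every row, so it overstates the risk once explants are part of the attrition.

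**Scale.** With constant dropout, follow-up is 160 × 0.20/0.1116 = about 287 person-years instead of 320 (0.1116 is the yearly dropout hazard, 0.2231/2). A gap of 2.0 points is 1.2 subjects in 60 or 3.2 in 160. Exact 95% intervals are far wider: 12/60 gives 10.8% to 32.3%, and 32/160 gives 14.1% to 27.0%.

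**The case against.** The strongest reply is that the safety objective is descriptive. There is no safety hypothesis, threshold or performance goal, and no passage calls the percentage a 2-year risk. As the share of implanted subjects with a reported event during the study, it is accurate. The gap is also small against sampling error. Both points stand, and they limit the weight of this one. They do not make the crude percentage a sound basis for a 2-year statement: the bias has a known direction under independent loss, and long-term safety is what the study is for.

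Readers might infer stronger versions that the documents do not support:

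- *That safety is reported only as crude percentages of implanted subjects.* It is not. SAP 7.10 also plans event counts, listings and a death listing, and uses wider sets: "Serious AEs will be summarized for all consented subjects (Consent Subject Set), all subjects who go through lead placement procedure". SAP 7.1.1 tabulates discontinuation by visit with reasons, though without a link to the safety percentages.
- *That exit at explant itself causes the understatement.* A reportable event that leads to explant is captured before exit, and the crude figure is not biased low for a competing event. What can be lost is a late event of the explant procedure, which Protocol 11.1 counts as procedure-related. No reanalysis recovers that.
- *That the cohorts cannot be compared.* Protocol 13.1.1 expects the same attrition in each, SAP 7.5 treats them as independent, and no safety comparison between them is planned.
- *That the bias reaches about 17%, by placing all exits at 3 months.* This conflicts with the protocol's expectation of less than 10% by then.

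**Conclusion.** The point holds in a limited form. Post-implant safety percentages take every implanted subject as denominator and make no allowance for unequal follow-up. Read as 2-year risks, they are biased low if losses other than explant and death are unrelated to event risk.

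With 20% attrition and no explants in it, the relative bias is about 10% under constant hazards, 2% to 4% if events are mostly perioperative, and 13% to 16% if the hazard rises with time. It cannot exceed 20%. It shrinks as explants form more of the attrition and vanishes if they are all of it; the documents do not state the share. If subjects who leave have a different event risk from those who stay, the size, and possibly the direction, would change.

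No primary objective, test or decision rule is affected. This is a cheap improvement to the safety analysis.

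**What to change.** In SAP 7.10, keep the crude tables and listings as planned, and add:

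- Aalen-Johansen cumulative incidence from implant to first ADE and to first SADE at 3, 6, 12 and 24 months, by cohort and pooled;
- death and permanent explant as competing events, with an event on or before the day of explant counted as an event, and all other exits censored;
- numbers at risk and 95% confidence intervals at each time;
- a sentence saying that any 2-year safety statement rests on these estimates.

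The SAP should also say how completers are handled near the last time point. The two-year window opens at 104 weeks − 28 days = 100 weeks, and subjects exit after that visit, so few may still be at risk at exactly 24 months.

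The dates needed are already within the planned data: event dates (Protocol 11.2), the Study Exit form (Protocol 9.9), and the implant date from which visit windows run (Protocol 9.1). The cost is a few lines of SAP text and one more table, and the reported percentages will be slightly less favourable.
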